School of Experimental Psychology
[name]
[name]
United Kingdom

[name] t.
[name] f.
[contact]
www.bristol.ac.uk

STUDY PROTOCOL

Are cognitive deficits associated with tobacco abstinence mediated by nicotine withdrawal?

[name], [name], [name], [name], [name],
[name]

Background

Smokers report cognitive deficits following tobacco withdrawal, which may contribute to the withdrawal syndrome and subsequent relapse. However, it is unclear whether these deficits are primarily due to the effects of nicotine withdrawal or other mechanisms such as expectancies about the effects of abstaining or the loss of sensorimotor stimulation.

In a systematic review of the literature we identified several cognitive tasks sensitive to a period of acute abstinence ([name] et al., under review). We now wish to determine whether these effects are indeed mediated via nicotine withdrawal. We will do this by comparing task performance of abstinent smokers receiving nicotine replacement therapy (NRT) with abstinent smokers receiving placebo NRT. We expect that performance of abstinent smokers receiving NRT will be different (and more similar to performance of satiated smokers) than performance of abstinent smokers receiving placebo NRT.

Since nicotine withdrawal is known to be dynamic and complex, and fluctuates over time, it is not well captured by a single assessment (Hughes 2007, Bedi, Preston et al. 2011, Adams and [name] 2013). We will use ecological momentary assessment to measure craving of participants via an Android mobile device at several time points over the course of a single day, as participants are in their natural environment.

Study Objective and Hypotheses

We propose to examine the effects of nicotine delivered via NRT on cognition and craving in acutely abstinent smokers. The principal research question to be addressed is:

Are changes in cognitive performance and craving levels due to acute tobacco abstinence mediated by nicotine withdrawal?

We hypothesize that abstinent smokers receiving active NRT will display less impairment in cognitive task performance than abstinent smokers who receive placebo NRT. We also hypothesise that craving assessed via EMA will be higher in abstinent smokers receiving placebo than in abstinent smokers receiving NRT.

Study Design

In this laboratory-based within-subjects study participants will attend two sessions. Before both sessions, participants will be asked to abstain from smoking overnight and until the end of the testing day. For one session, participants will be asked to apply an active nicotine patch 30 minutes before the behavioural assessment and use a nicotine nasal spray *ad libitum*. For the other session participants will be asked to apply a placebo patch and will receive placebo nasal spray. Participants will be blinded as to which treatment they receive. The order of the sessions will be counterbalanced across participants.

On each testing day, the behavioural assessments will be completed in the morning, with the order of the cognitive computer-tasks counterbalanced across participants and fixed within participants. After testing, participants will be provided with an Android mobile device to measure craving for another six hours, using a specifically programmed app. The assessment of craving can be done remotely, so participants can leave the testing site. After six hours participants will be asked to return the mobile device and the nasal spray to the researcher, have their abstinence confirmed via breath test and their patch removed.

Study Site

School of Experimental Psychology, University of Bristol, [name], United Kingdom.

Participants and Recruitment

We will recruit individuals aged 18 to 60 years, who are regular smokers from the staff and students of the University of Bristol and from the general population.

Participants will be recruited by existing email lists, posters, flyer advertisement, and by word of mouth. After contacting the research coordinator and reading the study information sheet, participants will complete an initial online screening form. Those who meet the inclusion and exclusion criteria will be contacted by the research coordinator to arrange a testing session. Participants will be reimbursed £80 for their

time and expenses.

Inclusion criteria

- 18-60 years old.
- smoke at least 5 cigarettes per day.
- smoke first cigarette within one hour of waking.
- smoking for at least 6 months.
- English as first language (or equivalent level of fluency).
- visual acuity within normal limits.
- willingness to abstain from smoking for about 20 hrs on two occasions, once with using nicotine patch and nasal spray and once using placebo nicotine patch and nasal spray without being made aware of the order of the conditions at any point of the study.
- if female: willingness to take a pregnancy test before each study session.

Exclusion criteria

- currently taking any psychoactive medication
- actively trying to give up smoking
- history of substance/alcohol misuse or dependence (other than nicotine or cannabis)
- if female: pregnant, breast feeding or trying to conceive
- having extensive dermatitis/other skin disorder that precludes patch use
- having had acute coronary syndrome or a stroke within the past three weeks
- allergic to any component of the nicotine replacement therapy patch or nasal spray

Sample size determination

We will require 70 participants to achieve 80% power and an alpha-level of 0.5, in order to detect the smallest effect size indicated in our recent meta-analysis ($d = 0.34$ for the delay-discounting task) ([name] et al., under review). The smallest effect size available was used in order to provide the most conservative sample size estimate. For the cognitive task with the largest effect size ($d = 0.59$ for the n-back task), a sample size of 25 participants would suffice (Mendrek et al., 2006).

Withdrawal of participants

Participants will be informed that they are able to withdraw from the study at any time. In the case of an adverse event, that is any unforeseen or serious reaction to the procedure or the NRT products, participants will be given full reimbursement of £80. In the case of the participant not tolerating the NRT product by displaying any of the harmless side effects described below, participants will be reimbursed £35 if this occurs in the first session, and £80 if this occurs in the second session. In the case of the researcher being unable to track the eyes of the participant they will be reimbursed a monetary amount that is commensurate with the time they have spent in the laboratory (e.g., stopping half way through the first session would result in a reimbursement of 25%).

Randomisation

The order of sessions (placebo, NRT) will be counterbalanced. The order of the cognitive tasks during the laboratory session will be randomized across participants, and fixed within participants.

Measures and Materials

- Working memory performance (number of commission errors) as measured by the n-back task
- Cognitive bias (dwell time and reaction times) as measured by an eye-tracking dot probe task
- Reward choice (area under the curve; AUC) as measured by the delay-discounting task
- Craving measured via ecological momentary assessment using a mobile device

Questionnaires

Questionnaire measures will comprise the Fagerström Test of Nicotine Dependence (FTND) (Heatherton, Kozlowski et al. 1991), the Readiness to Quit Ladder (Biener and Abrams 1991), the Minnesota Nicotine Withdrawal Scale-self report (Hughes and Hatsukami 1998), and the Questionnaire of Smoking Urges – Brief (Tiffany and Drobes 1991).

Delay-discounting task

Participants are made aware at the start of the task that the amounts of money will be hypothetical and no real money will be gained in this task. Participants are asked to make 91 choices between a standard hypothetical amount of money (£100) available after one of five delays (0, 7, 30, 90, or 180 days) and one of 23 alternative hypothetical amounts available immediately (“Which would you prefer: £100 in 180

days or £30 now?”). Question order is randomized.

N-back task

Participants are required to decide whether each stimulus in a sequence matches the one that appeared *n* items ago. A 2-back and 3-back condition is used. Eight phonologically-distinct letters will be used as stimuli (*B, F, H, K, M, Q, R, or X*). Response time and accuracy of responses will be recorded. Each condition (2-back and 3-back) will be presented in 4 blocks, which will each consist of 48 trials and 2 additional practice blocks of 20 trials. Each trial begins with a central fixation cross, presented for 500 ms, followed by the stimulus in that location for 500 ms and a 2000 ms inter-stimulus interval. Participants will be asked to make a “yes”/”no” response via button press as quickly and accurately as possible.

Go/no-go task

Participants are required to make a response (press button) when a designated “go” cue is presented and withhold responding to a designated “no-go” cue. At the start of each trial a fixation cross is displayed for 500 ms. The cues will be shapes (arrow or star) presented in the centre of a screen for 1000 ms. A practice phase of 6 trials will be implemented, where participants will receive feedback on their performance. The first 20 trials will be go-trials to build a pre-potent response and the remaining 90 trials will be made up of 30 no-go trials and 60 go-trials, presented in randomized order.

Dot-probe task

Participants are presented with two stimuli (photographs), one of which is neutral and one of which is related to smoking. Each trial starts with a central fixation cross shown for 1000 ms, which is followed by a side by side presentation of a pair of the stimuli for 2000 ms. 120 main trials will be presented, of which 80 will be critical trials, including a neutral and a smoking related picture and 40 will be filler trials including neutral pictures only. After presentation of the pictures a dot will appear on one side of the screen, in the former location of one of the two pictures. Participants are instructed to indicate the location of the dot as fast as possible via button press. Eye-movements towards these locations on the screen will be recorded from the start of the fixation cross until a button press has been made. There will be 14 practice trials before the start of the main trials.

Ecological momentary assessment

After completion of the laboratory testing session participants will be given an Android mobile device with ecological momentary assessment software installed on it. The software will randomly alert participants over the next six hours to respond to the following questions:

- Able to focus? (yes, no)
- Alert? (yes, no)

- Angry/frustrated? (yes, no)
- Bored (yes, no)
- Calm/relaxed? (yes, no)
- Difficulty concentrating? (yes, no)
- Enthusiastic? (yes, no)
- Happy? (yes, no)
- Irritable? (yes, no)
- Miserable? (yes, no)
- Nervous/tense? (yes, no)
- Quiet/sleepy? (yes, no)
- Restless? (yes, no)
- Sad? (yes, no)
- Cigarette craving? (yes, no)

Participants will furthermore be asked to indicate the highest craving they experienced since the last prompt.

Procedures

Participants will be scheduled to arrive in the laboratory between 8.00 a.m. and 11.00 a.m. Two appointments will be scheduled, at least one week apart. Upon arrival at the first session, participants will be given the opportunity to read the information sheet and ask any questions about the study. The researcher will verbally confirm the schedule of the study and will remind them that they can stop the study at any time without having to give a reason. The participant will complete two copies of the informed consent form, one of which they are able to take away and the other will be filed in the study master file.

The following procedures will be used on both occasions if not indicated otherwise. If the participant is female a pregnancy test will be administered. Participants' breath CO level will be measured and participants will then complete the questionnaires. Following this, the nicotine (or placebo) patch will be administered by the researcher on the participant's arm. The participant will then be instructed to use the nicotine (or placebo) nasal spray once and will be asked to wait for 30 minutes so the nicotine can take its effect. They will then be asked to complete the four cognitive tasks.

After completion of the behavioural assessments, participants will be provided with a mobile device and instructed how to use the mobile device application in order to assess craving. They will be asked to remotely indicate craving levels on the device whenever they are prompted to do so. Craving will be assessed at random intervals for six hours. Participants will be instructed to bring the device as well as the nasal spray back to the testing site at the end of this period, where continued abstinence will be tested via breath test and participant will complete the Questionnaire of Smoking Urges- Brief (Tiffany & Drobes, 1991) once more. The patch will then be removed by the researcher. Participants will be debriefed and reimbursed for their time and expenses, after the completion of the second test day.

Drug Administration

The strength of the active nicotine patch will be 14 mg. Both active and placebo patches will be applied by the researcher 30 minutes before the start of the testing session. The strength of the active nicotine nasal spray will be 10 mg/ml. The participant will be instructed how to use the nasal spray by the researcher. Each nasal spray canister will contain 1 ml of nicotine nasal spray or placebo nasal spray. All NRT will be locked in a storage cupboard and be kept in a locked room.

Statistical Plan

Delay-discounting task

Indifference points will be derived and will be used to calculate area under the curve (AUC), using the following equation: $(x_2 - x_1)[y_1 + y_2/2]$, where x_2 and x_1 represent successive delays to receiving the standard and y_1 and y_2 the indifference point values associated with these delays. Smaller AUC values indicate greater discounting and impulsive choice (Mitchell 1999, Ashare and Hawk Jr 2012). The principal statistical analysis will be a one-way ANOVA of AUC values, with nicotine (active, placebo) as a within-subjects factor.

N-back task

The principal statistical analysis will be a one-way ANOVA of hit rates, with nicotine (active, placebo) as a within-subjects factor.

Go/no-go task

The principal statistical analysis will be a one-way ANOVA of commission error data, with nicotine (active, placebo) as a within-subjects factor.

Dot-probe task

The principal statistical analysis will be a 2 by 2 repeated measures ANOVA of eye movement dwell time data, with picture type (smoking, neutral) and nicotine (active, placebo) as within-subjects factors.

Ecological momentary assessment

Cigarette craving will be analysed using Generalized Estimation Equations in order to determine differences between the active and placebo NRT conditions.

Ethical Considerations and Informed Consent

Ethics approval has been obtained from the Faculty of Science Research Ethics Committee at the University of Bristol. The study will be conducted according to the revised Declaration of Helsinki (2013) and the 1996 ICH Guidelines for Good Clinical Practice E6 (R1). The investigator will explain the nature, purpose and risks of the study to the participant. The participant will receive the information sheet in

advance of the study session. There will be no time restriction on how long participants take to respond, with the exception that participants who respond after all study places have been filled will not be offered a place on the study. Therefore, participants will be given sufficient time to read the information and consider any implications, and to raise any questions with the investigators prior to making a decision to participate. On arrival at the study session participants will be given the opportunity to read the information sheet again and ask the investigator any questions. Written consent will then be obtained. Participants will be informed that they are free to withdraw at any time.

Safety

There are no expected hazards. Discomfort due to cigarette abstinence might be experienced. This will not exceed the discomfort experienced in any regular smoking-cessation attempt for this amount of time.

The study medication (NRT) is a licensed smoking cessation aid and available over the counter. It has been associated with some side effects. The more common side effects of both the patch and the nasal spray are upset stomach, headache or dizziness. The nicotine patch may cause skin irritations on the site of the patch application. The nasal spray can lead to watery eyes, sneezing and coughing. Generally these side effects may cause discomfort but are not considered dangerous. Furthermore as nicotine is rapidly cleared from body any side effects will subside quickly once nicotine is removed.

Participants will be given information on the possible side effects of the drug, will be encouraged to report any effects that they feel and will be able to withdraw from the study at any time. Contra-indications are hypersensitivity to the drug. The dose we are administering is standard therapeutic dose prescribed for smoking cessation, and therefore is considered safe in healthy volunteers.

Adverse Event Reporting

Adverse events or adverse reactions will be documented at the end of the relevant session using an adverse event report, and will be recorded in the CRFs. The adverse event reports will be anonymised by unique study identifier and stored in the master file. Adverse events or adverse reactions will be followed up until resolved if possible. At the end of the study a safety report will be compiled and sent to the Principal Investigator (PI) listing all adverse events and adverse reactions. All procedures related to adverse events will follow the University of Bristol adverse events policies and procedures.

Data Management

All aspects of the Data Protection Act will be adhered to. Consent forms will be retained by the School of Experimental Psychology for a period of 10 years after study completion. In the event that a participant revokes authorisation to collect or use personal health information, the investigator retains the ability to use all information collected prior to the revocation of participant authorisation.

Anonymised study data

The case report forms (CRFs) and electronic data will be anonymised by a unique numeric identifier. CRFs will be stored in a locked office. All data requested on the CRF will be recorded. All missing data will be explained. If any entry errors are made, a single straight line will be drawn through the incorrect entry and the correct data entered above it; to correct such an error. All such changes will be initialled and dated. Once data from CRFs have been inputted into a data spreadsheet they will undergo a reliability check (20% check by independent researcher). If an error rate greater than 1% is obtained the data will be re-inputted in full and assessed again. After the data have been positively assessed, the CRFs will be destroyed in the School's confidential waste facility.

Original computer data files will be backed up on a secured University of Bristol network drive. At the end of the study, electronic study data (including finalised data sheet) will be transferred to a designated University of Bristol Research Data Storage Facility for long-term archiving. Study data will be kept for a minimum of 15 years. At the appropriate time the data sheet will be locked and made open using the University of Bristol Research Data Repository.

Screening documents and participant contact details

Screening documents, participant contact details and participant identifier logs will be stored separately in a study master folder and kept confidential. These will be kept in the study master folder for one year after study completion or until data are made open (whichever comes first), after which these documents will be destroyed. Failed screening documents will be shredded immediately using School's confidential waste facility.

Revoked data

If a participant decides that they do not want their data used after their participation they have the right to request that the data are withdrawn. They can request this up to one year after study completion or until the data are made open (whichever comes first).

Quality Control and Quality Assurance

The investigators will be responsible for data quality. After approximately 10% of data collection has been completed, the study will undergo an in-house quality assessment. During this monitoring process all CRFs and study documents will be assessed as well as the investigators laboratory management and participant engagement, and corrected where necessary.

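### The abstinence rule and its breath check cover smoke only, so other nicotine use breaks no stated rule, goes unrecorded and may dilute the active-placebo contrast

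*Protocol*

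**What the plan says.** The principal question (Protocol, Study Objective and Hypotheses) is: "Are changes in cognitive performance and craving levels due to acute tobacco abstinence mediated by nicotine withdrawal". It is answered by comparing active with placebo NRT in the same abstinent smokers.

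The rules that produce abstinence all concern smoking:

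- Instruction (Study Design): "Before both sessions, participants will be asked to abstain from smoking overnight and until the end of the testing day".
- Inclusion criterion: "willingness to abstain from smoking for about 20 hrs on two occasions", once on active and once on placebo products.
- Check on arrival (Procedures): "Participants' breath CO level will be measured and participants will then complete the questionnaires".
- Check after the six-hour craving assessment (Procedures): "continued abstinence will be tested via breath test".

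The six hours are spent away from the laboratory: "The assessment of craving can be done remotely, so participants can leave the testing site".

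No section bars, asks about or records e-cigarettes, smokeless tobacco or the participant's own NRT, and no nicotine or cotinine measurement is planned. The nearest exclusion is "actively trying to give up smoking". The exclusion for substance misuse or dependence exempts nicotine.

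**The concern.** To answer a question about nicotine withdrawal, the placebo day has to be free of nicotine as well as smoke. Breath CO marks combustion and does not respond to nicotine from a non-combusted product. A smoker who also vapes is therefore eligible, can vape in either unsupervised window, and still satisfies every rule in the protocol.

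On the placebo day, such use relieves the withdrawal that the comparison depends on. On the active day, it adds nicotine to a participant who already receives it. Either way the paired difference tends towards zero.

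The Background section names expectancy and loss of sensorimotor stimulation as the rival explanations, so a weak or null difference would be read as favouring them. Because other nicotine use is not recorded, the analysis could not show afterwards whether it contributed.

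**Working it through.** **1. Which outcomes are exposed, and when.** The order in Procedures is: arrival, breath CO, questionnaires, patch, one use of the spray, 30-minute wait, cognitive tasks, then six hours off site with the mobile device, then return.

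| Unsupervised window | Outcome affected | Treatment given that day? | Expected pattern of other nicotine use |
|---|---|---|---|
| Overnight to arrival | Cognitive tasks (and possibly craving) | No; participants are blinded | Similar on both days |
| Six off-site hours | EMA craving | Yes | Plausibly more on placebo, since the protocol hypothesises higher craving there |

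The off-site hours come after all cognitive testing on that day and cannot affect that day's task results.

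**2. Reproduce the planned sample size.** Inputs from Sample size determination: 80% power, d = 0.34 (delay discounting) and d = 0.59 (n-back). With a paired t-test, the noncentrality is d × √n on n − 1 degrees of freedom. At two-sided 0.05:

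- d = 0.34: the smallest n is 70, with power 80.1%.
- d = 0.59: the smallest n is 25, with power 80.8%.

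Both stated sample sizes reproduce. The alpha printed in the protocol is 0.5, which would give 19 for d = 0.34, so 0.05 is used below; that misprint is a separate matter. For d = 0.34, 70 is the exact minimum and has no reserve.

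**3. Dilution.** Let f be the share of participants affected and L the share of the contrast that each of them loses. With the SD of the paired difference held fixed:

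d_eff = d × (1 − f × L)

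Neither f nor L is given in the documents; both are assumptions. Power at n = 70, two-sided 0.05:

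| Assumed f | d_eff, L = 1 (d = 0.34) | Power | d_eff, L = 0.5 (d = 0.34) | Power | d_eff, L = 1 (d = 0.59) | Power |
|---|---|---|---|---|---|---|
| 0% | 0.340 | 80% | 0.340 | 80% | 0.590 | 99.8% |
| 5% | 0.323 | 76% | 0.3315 | 78% | 0.5605 | 99.6% |
| 10% | 0.306 | 71% | 0.323 | 76% | 0.531 | 99.2% |
| 20% | 0.272 | 61% | 0.306 | 71% | 0.472 | 97% |

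Example: f = 0.20 and L = 1 give 0.34 × 0.80 = 0.272. Under total loss, restoring 80% power for delay discounting would take 78, 86 or 109 participants at 5%, 10% or 20%.

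**4. EMA craving.** The protocol gives no planning effect for this outcome, so no power figure can be derived. Only the direction, towards zero, can be stated.

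**The case against.** **Removal of the contrast.** A reader might infer that other nicotine use removes the nicotine contrast altogether. The documents do not support that. A participant who vapes before both sessions still receives active products on one day and placebo on the other. The Safety section describes nicotine as quickly cleared, and the arrival procedures and the 30-minute wait precede testing. The contrast is reduced for that participant and diluted for the trial, so the L = 1 columns are a worst case.

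**One-sided leak.** A reader might also infer that use is concentrated on the placebo day for every outcome. Overnight use precedes a blinded treatment, so placebo-day craving cannot drive it. The one-sided argument fits only the EMA hours, and the power figures for delay discounting say nothing about those hours.

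**Prevalence.** The documents contain no rate of vaping or other nicotine use. Excluding people who are trying to quit probably removes some users of their own NRT, which narrows the gap. It does not remove smokers who vape without intending to quit.

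**Unseen documents.** The information sheet and online screening form are not shown and may contain a wider instruction. If they do, the practical problem is smaller, but the protocol's own instruction and criterion would still need to match them.

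**Existing safeguard.** Withdrawal and urge questionnaires are completed before the patch at each session and give some indication of the participant's state on arrival. They do not ask about nicotine use in the unsupervised hours, and no rule ties them to eligibility for the session.

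These objections limit the size and mechanism of the problem. They do not close the gap between a question about nicotine and a rule about smoke.

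**Conclusion.** The point holds as a risk of dilution. As written, the protocol permits non-combusted nicotine on the placebo day and has no means of recording it. Eligibility, participant instructions and abstinence checks are protocol content, and an SAP cannot recover information that was never collected.

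The size is unknown. For delay discounting at n = 70, power would lie between 78% (5% affected, half the contrast lost) and 61% (20% affected, all of it lost), against a planned 80%. For n-back it stays at about 97% or more throughout. These figures rest on an assumed prevalence, an assumed loss per affected participant, a fixed SD and a two-sided 0.05 level.

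The documents do not support a conclusion that a null result would be uninterpretable, or that the placebo condition will contain nicotine. They support only that this could happen without breaking a stated rule and without being seen. A cheap improvement is warranted.

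**What to change.** 1. Reword the instruction in Study Design and the matching inclusion criterion to require abstinence from smoking and from every other nicotine source (e-cigarettes, smokeless tobacco, own NRT), overnight and until the end of each testing day, apart from the study patch and spray. Align the information sheet if it differs.
2. On arrival, before the patch, ask about any such use since abstinence began, and rebook the session if there was any. This use precedes that session's blinded treatment, so rebooking does not select on the response to it.
3. On return, ask again about the six off-site hours and record the answer.
4. Keep all participants in the main analysis. Report EMA-period use by condition. Do not rely on an EMA analysis that drops the affected days: such use comes after treatment and may be caused by placebo craving, so dropping those days could remove the highest-craving placebo days and bias the contrast.

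The cost is changed wording, two self-report questions per session, a few rebooked sessions and possibly the loss of some participants who also vape. Self-report cannot be confirmed by the breath test, so the change reduces the gap and makes use visible but does not guarantee a nicotine-free placebo day.

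### Failure to track the eyes appears to end participation, although only dot-probe dwell time needs eye-tracking and the 70 has no allowance for loss

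*Protocol*

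**What the plan says.** The Protocol deals with eye-tracking failure in Withdrawal of participants, next to adverse events and intolerance of the study product: "In the case of the researcher being unable to track the eyes of the participant they will be reimbursed a monetary amount" that reflects the time spent in the laboratory. Its example is that "stopping half way through the first session would result in a reimbursement of 25" per cent. Full payment for the study is £80.

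The other relevant places are these.

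- **Sample size determination:** "We will require 70 participants to achieve 80% power and an alpha-level of 0.5", for the smallest effect in the sponsor's meta-analysis, d = 0.34 for delay discounting. For n-back, d = 0.59 and 25 participants are given. No loss rate or replacement rule appears.
- **Procedures:** after the patch, one use of the spray and a 30-minute wait, "They will then be asked to complete the four cognitive tasks". Craving is then recorded on a mobile device for six hours.
- **Measures and Materials; Dot-probe task:** eye movements are recorded in the dot-probe task and nowhere else. That task also yields button-press reaction times.
- **Randomisation:** task order varies between participants and is fixed within each one.
- **Statistical Plan:** the four task analyses are within-subject ANOVAs. The dot-probe analysis uses dwell time. Craving is analysed by GEE.

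**The concern.** A technical failure that affects one measure appears to end collection of all the others. Delay discounting, n-back, go/no-go and craving need no eye-tracking, and craving is part of the principal research question. Delay discounting is also the outcome on which the sample size rests.

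In a two-session within-subject design, someone who leaves during session one contributes nothing to a paired comparison, even for tasks already finished that day. Momentary assessment starts only after laboratory testing, so a stop part-way through session one also yields no craving data. A later analysis plan cannot repair this, because the data would never have been collected.

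The second issue is the meaning of the 70. If it is the number enrolled and nobody is replaced, any such loss takes delay discounting below its planned power.

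**Working it through.** **1. Does the payment example imply stopping?** There are two sessions. Half of one session is 0.5 × 1/2 = 0.25 of the study, which matches the 25% in the example (0.25 × £80 = £20). The example works only if the rest of session one and all of session two do not take place.

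**2. What is lost, by when the failure is met?**

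| Failure first met in | Delay discounting, n-back, go/no-go | Craving |
|---|---|---|
| Session one | No pair for any task, including those already done | None if stopped before momentary assessment starts |
| Session two | Complete pairs for tasks placed before the dot-probe, none for those placed after it | Session-one data exist and could enter the GEE |

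**3. Reproducing the 70.** Inputs from Sample size determination: d = 0.34, power 80%, n = 70; and d = 0.59, n = 25. Sidedness is not stated. The method is a paired t-test, equivalent to a two-level within-subject ANOVA, with df = n − 1 and noncentrality d√n:

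power = P(|T| > t for 1 − α/2, df = n − 1), where T is noncentral t with parameter d√n.

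- Two-sided α = 0.05, d = 0.34: smallest n is 70, with noncentrality 0.34 × √70 = 2.84 and power 80.1%. This matches.
- Two-sided α = 0.05, d = 0.59: smallest n is 25. This matches.
- One-sided α = 0.05: n = 55 and 20. Neither matches.
- α = 0.5 as printed: n = 19 for d = 0.34, or 98.5% power at n = 70. This does not match.

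Two-sided 0.05 is therefore assumed from here on. Since 69 gives 79.5%, the 70 is the bare minimum and contains no margin.

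**4. Power if stopped participants are not replaced.** The Protocol gives no failure rate, so the losses below are assumptions.

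| Pairs left | Lost of 70 | Power, delay discounting (d = 0.34) | Power, n-back (d = 0.59) |
|---|---|---|---|
| 70 | 0 | 80.1% | 99.8% |
| 69 | 1 | 79.5% | 99.8% |
| 66 | 4 (about 5%) | 77.7% | 99.7% |
| 63 | 7 (10%) | 75.7% | 99.6% |
| 56 | 14 (20%) | 70.5% | 99.1% |

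**5. Two ways to hold the 70.** If affected participants stay in for the outcomes that need no eye-tracking, this cause removes no delay-discounting pairs and power stays at 80.1%. If they are stopped in session one, recruitment must rise to 70/0.95 = 73.7, so 74, at 5% loss, or 70/0.90 = 77.8, so 78, at 10%.

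**The case against.** The strongest reply is that the sentence fixes a payment and nothing more. It does not order the participant to stop or the remaining tasks to be skipped. A reader might infer that such a participant is lost from the whole study and that the data are thrown away. The documents do not support that. No section directs removal of data after a tracking failure; Data Management covers only revoked authorisation and requests to withdraw data. A failure first met in session two can also leave usable data.

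A reader might also infer that 80% power is unattainable unless everyone enrolled completes. That does not follow either. The sentence "We will require 70 participants to achieve 80% power" does not say whether the 70 are enrolled or completing, and replacing those who leave would keep power at 80.1%.

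The size is hypothetical as well. The visual-acuity criterion may keep failures few, and only delay discounting is shown to be sensitive. Stopping early and replacing has some merit: it keeps one common sample across tasks and spares the participant a second long abstinence. The retained reaction times would add little, since the principal dot-probe analysis is dwell time.

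These points limit the wording and the size of the concern. What remains is that the section heading and the 25% example make early exit the natural reading. Even with replacement, obtainable data on the other outcomes would be given up without a stated reason.

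**Conclusion.** The point holds as a cheap improvement to the design and a needed clarification. The Protocol implies that participation ends when the eyes cannot be tracked, although this affects only dwell time. It does not say whether the participant may continue, whether they are replaced, or what the 70 counts.

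The effect on power is conditional. It arises only if the 70 are enrolled participants without replacement, and it assumes two-sided α = 0.05. Delay discounting then has 79.5% power after one lost pair, 77.7% after four and 75.7% after seven. The true failure rate is unknown. For n-back the loss is immaterial, with power of at least 99.1% even at 56.

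**What to change.** In Withdrawal of participants, state that inability to track the eyes makes only dwell time missing, and that the participant is invited to continue with the other tasks, the momentary assessment and the second session. Keep pro-rata payment for those who choose to leave. In Sample size determination, define the 70 as participants completing both sessions, and correct or explain the printed "an alpha-level of 0.5", since the figure reproduces only with 0.05.

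The cost is the full £80 and the laboratory time for the few affected. Dwell time would be analysed on slightly fewer people than the other outcomes. If the sponsor prefers that such participants leave, the alternative is to say so, state that they are replaced, and recruit accordingly (74 or 78 at assumed losses of 5% or 10%).
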